9.8 Multiplicity

No adjustment will be made for multiplicity.

9.9 Sample Size and Power Calculations

166 participants (83 in each group) will be randomized in this study, and the expected drop-out rate is 15%. Then 140 evaluable participants (70 participants in each group) will provide 84% power to detect a difference of 1 point between MK-7264 and placebo during TRC2, in change from baseline of the average daily pelvic pain score in the NRS, with one IA conducted when 84 participants have been enrolled and completed TRC2 or 60% of the participants who are expected to complete TRC2. This power calculation is based on a two-sided test with Type I error 0.05. The drop-out rate is from previous trials in chronic cough of MK-7264, and there is limited data to estimate the drop-out rate for ERP. [Table 7](#) provides the power calculations for different assumptions of drop-out rate with the randomized participants.

Table 7 Power Calculation Based on Different Dropout Rates

Number of Randomized Participants	Dropout Rate	Number of Evaluable Participants	Power
166	10%	149	86%
	12%	146	85%
	15% (expected)	140	84%
	20%	132	82%

The assumption of the 1 point difference between MK-7264 and placebo, and the common standard deviation (SD) of 2 units are based on a publication by Diamond [Diamond, M. P., et al 2013]. Table 8 provides the power calculations for different assumptions of SD with the sample size.

Table 8 Power Calculation for Different Assumptions of SD with 140 Evaluable Subjects

Difference	SD	power
1	2.5	66%
1	2	84%
1	1.5	98%
1	1	100%

9.10 Subgroup Analyses

Analysis for the primary and secondary efficacy endpoints will be provided for the following subgroups of baseline factors:

- Age category (18 – 30, 31 – 49 years).
- Pain intensity: NRS in the eDiary moderate (score: ≥ 5 to <8) and severe (score: ≥ 8) at baseline.
- Geographic region (US versus ex-US)

Additional subgroup analysis will be provided for change from baseline in average daily use of rescue medication by geographic region (US versus ex-US).

9.11 Compliance (Medication Adherence)

For each participant, percent compliance will be calculated using the following formula:

$$\text{Percent Compliance} = \frac{\text{Number of Days on Therapy}}{\text{Number of Days Should Be on Therapy}} \times 100\%$$

A day within the study will be considered an “On-Therapy” day if the participant takes all required medication. When a participant takes less than or more than the required medication on a day, that day is not considered an “On-Therapy” day.

For participants who are followed for the entire study period, the “Number of Days Should be on Therapy” is the number of days from the first scheduled treatment day to the last scheduled treatment day. For participants who discontinue from the study, the “Number of Days Should be on Therapy” is the number of days from the first scheduled treatment day to the last dose day.

Summary statistics will be provided on percent compliance for the APaT population.

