4 STUDY DESIGN

4.1 Overall Design

Specific procedures to be performed during the study, as well as their prescribed times and associated visit windows, are outlined in the SoA in Section 1.3. Details of each procedure are provided in Section 8.

This is a randomized, placebo-controlled, parallel-group, multi-site, double-blind, efficacy and safety study of MK-7264 in participants with moderate to severe ERP (cyclic and non-cyclic).

The study will be approximately 24 weeks in duration for each participant, and include 1 menses during screening before Visit 2, followed by 5 complete menstrual cycles, as detailed below:

- One SC during the screening period:
 - Starts at Visit 2, 1 day after the last day of the previous menses
- One BC during the single-blind, placebo run-in period:
 - Starts at Visit 3, 1 day after the last day of the SC menses
- TRC1 and TRC2 after randomization:
 - Start at Visit 4 or 5, 1 day after the last day of the BC or TRC1 menses, respectively.
- One PTC after the participant has stopped taking study intervention (ie, completed TRC2), but may continue to use rescue medication:
 - Starts at Visit 6, 1 day after the last day of TRC2 menses.
 - A telephone contact will occur approximately 14 days after Visit 6.
 - Visit 7 occurs 1 day after the last day of PTC menses

At Visit 2, participants will receive the eDiary which will be used daily through the end of the study to collect pelvic pain score, vaginal bleeding/non-bleeding days, use of naproxen sodium rescue medication, any use of pain relief medication other than the naproxen sodium provided by the Sponsor, and impact of pelvic pain.

This study will use a group sequential design based on prespecified criteria. There will be 1 futility interim analysis (IA). The IA will be conducted when 84 participants have completed TRC2 (ie, 60% of the participants who are expected to complete TRC2). Results of the IA will be reviewed by the Standing Internal Data Monitoring Committee (SiDMC), which will make recommendations to continue or end the study according to the plan described in Section 9 - Statistical Analysis Plan and in a separate SiDMC Charter (see more information in Section 10.1.4.1).

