Note: Pain severity score will be measured using 0-10 NRS anchored with 0 (no pain) and 10 (extremely severe pain).

12. Participant has demonstrated compliance with $\geq 75\%$ of daily eDiary entries (ie, pelvic pain score, vaginal bleeding, rescue medication intake, intake of pain relief medication other than naproxen sodium provided by Sponsor, and impact of pelvic pain) during the SC.

Note: eDiary compliance will be automatically calculated by the eDiary vendor partner and a report will be provided. The investigational site should review the report before the participant's scheduled visit to assess eligibility.

13. Participant has taken only the study provided rescue medication, at a dose not exceeding the maximum dose determined by the investigator according to the local label, for control of ERP during the SC as evidenced in the eDiary.

Note: Short term use (ie, ≤ 3 days) of other non-opioid pain medications for acute conditions other than ERP is permitted.

At Visit 4 (Before Randomization)

14. Participant's menstrual cycle before Visit 4 (BC) was 24 to 38 days (inclusive) as documented in the eDiary.
15. Participant reports at least moderate pelvic pain during the BC as defined by average daily pelvic pain (cyclic and non-cyclic) score ≥ 5 .

Note: Pain severity score will be measured using 0-10 NRS anchored with 0 (no pain) and 10 (extremely severe pain).

16. Participant has demonstrated compliance with $\geq 75\%$ of daily eDiary entries (ie, pelvic pain score, vaginal bleeding, rescue medication intake, intake of pain relief medication other than naproxen sodium provided by Sponsor, and impact of pelvic pain) during the BC.

Note: eDiary compliance will be automatically calculated by the eDiary vendor partner and a report will be provided. The investigational site should review the report before the participant's scheduled visit to assess eligibility.

17. Participant is $\geq 80\%$ compliant with the placebo run-in medication (as determined by site-performed tablet count).
18. Participant has taken only the study provided rescue medication, at a dose not exceeding the maximum dose determined by the investigator according to the local label, for control of endometriosis-related pelvic pain during the BC as evidenced in the eDiary.

Note: Short term use (ie, ≤ 3 days) of other non-opioid pain medications for acute conditions other than ERP is permitted.

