6.4 Study Intervention Compliance

Records of treatment compliance for each participant will be kept during the study. Compliance will be based on tablet count. In cases in which tablet count cannot be performed, participant reporting will be used to assess compliance. Issues with compliance should be discussed with the participant and addressed as deemed appropriate by the investigator.

Interruptions from the protocol specified treatment plan in which a participant's compliance is $< 80\%$ require consultation between the investigator and the Sponsor and written documentation of the collaborative decision on participant management.

Sponsor consultation and written documentation of collaborative decision on participant management is not required if reason for $< 80\%$ compliance is due to an AE. Such instances of $< 80\%$ compliance will not be considered a protocol deviation. Consultation should occur in a timely manner upon site learning of poor study intervention compliance. While awaiting Sponsor feedback, the investigational site should conduct participant counseling regarding importance of study intervention adherence, and the investigator can dispense study

intervention after such counseling, if in their medical judgment, the participant is able to comply moving forward with study intervention instructions.

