7 DISCONTINUATION OF STUDY INTERVENTION AND PARTICIPANT WITHDRAWAL

7.1 Discontinuation of Study Intervention

Discontinuation of study intervention does not represent withdrawal from the study.

As certain data on clinical events beyond study intervention discontinuation may be important to the study, they must be collected through the participant's last scheduled follow-up, even if the participant has discontinued study intervention. Therefore, all participants who discontinue study intervention prior to completion of the protocol-specified treatment period will still continue to participate in the study as specified in Section 1.3 and Section 8.10.5.

Participants may discontinue study intervention at any time for any reason or be discontinued from the study intervention at the discretion of the investigator should any untoward effect occur. In addition, a participant may be discontinued from study intervention by the investigator or the Sponsor if study intervention is inappropriate, the study plan is violated, or for administrative and/or other safety reasons. Specific details regarding procedures to be performed at study intervention discontinuation are provided in Section 8.10.5.

A participant must be discontinued from study intervention but continue to be monitored in the study for any of the following reasons:

- The participant or participant's legally acceptable representative requests to discontinue study intervention.
- The participant's treatment assignment has been unblinded by the investigator, MSD subsidiary, or through the emergency unblinding call center.
- The participant has a medical condition or personal circumstance which, in the opinion of the investigator and/or Sponsor, places the participant at unnecessary risk from continued administration of study intervention (including recommendation to discontinue participant from study treatment as part of monitoring for crystalluria/urolithiasis, see Section 8.3.8.1–Renal and Urological Safety Procedures).

- The participant has a confirmed positive serum pregnancy test.
- In case of clinically significant and potentially drug-related rash or signs and/or symptoms consistent with allergic drug reaction or anaphylaxis to study treatment.

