For participants who are discontinued from study intervention but continue to be monitored in the study, all visits and procedures, as outlined in the SoA, should be completed. Section 8.10.5 describes the procedures to be completed at each specified visit.

Discontinuation from study intervention is “permanent.” Once a participant is discontinued, he/she shall not be allowed to restart study intervention.

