8.6 Pharmacokinetics

The date and time for the last dose of study treatment taken before the study visit on which the PK sample was collected should be recorded in the eCRF. In addition, the date and time of the PK sample collection should also be recorded in the eCRF.

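### Does the exact-dose-day compliance formula need replacing, given that the protocol describes tablet counts and no daily study-drug record?

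*Combined protocol and SAP*

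**What the plan says.** Section 9.11 defines percent compliance as days on therapy divided by days that should be on therapy. The numerator is strict: "When a participant takes less than or more than the required medication on a day, that day is not considered an" on-therapy day. For a woman followed for the whole study, the denominator runs from the first to the last scheduled treatment day. For a woman who discontinues from the study, it "is the number of days from the first scheduled treatment day to the last dose day". Section 9.12 measures treatment duration by days on therapy and does not say whether the exact-dose meaning carries over. sSAP 3.11 and 3.12 repeat both sections unchanged.

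Other sections describe the data:

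- Section 6.4: "Compliance will be based on tablet count", with participant reporting as the fallback when a count cannot be done.
- Section 5.1, criterion 17: run-in compliance of at least 80%, "as determined by site-performed tablet count".
- Section 4.1: an "eDiary which will be used daily through the end of the study to collect pelvic pain score, vaginal bleeding/non-bleeding days", followed by rescue use, other pain relief and impact of pain. Study tablets are not listed.
- Section 8.6: "The date and time for the last dose of study treatment taken before the study visit" is recorded for visits with a PK sample.
- Section 8.1.13: the morning dose on site-visit days is witnessed.

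On stopping drug, Section 7.1 says that "all participants who discontinue study intervention prior to completion of the protocol-specified treatment period will still continue to participate in the study", and also that "Once a participant is discontinued, he/she shall not be allowed to restart study intervention".

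**The concern.** The numerator needs to know what was taken on each day. A tablet count at a visit gives a total over several weeks and cannot say how missed tablets were spread. If the count is the only source, the percentage in Section 9.11 cannot be computed from it.

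The denominator raises a second question. The protocol deliberately keeps women who stop drug in follow-up. Read literally, they are followed for the entire study and get the full-schedule denominator, while women who leave the study get a denominator that ends at the last dose. The same dosing history could then give very different percentages.

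Third, if days on therapy in Section 9.12 has the Section 9.11 meaning, a day with one tablet adds nothing to treatment duration.

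At stake is how well a reader of a proof-of-concept result, especially a null one, can judge how much drug was taken. Two programmers could report different figures for the same woman.

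**Working it through.** The documents give no compliance figure to reproduce, so the check is how far apart the readings can lie.

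**Inputs.** Two tablets a day (Section 8.1.13). About 8 weeks of treatment (Section 8.1.13.1), taken here as D = 56 days and 112 tablets; this is an assumption. Range of treatment length: two cycles of 24 to 38 days, the eligibility range in Section 5.1, so 48 to 76 days. This assumes that treatment cycles stay within that range.

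**Count against day rule.** With m tablets missed and never more than two taken in a day, day-based compliance lies between (D − m)/D (each missed tablet on a separate day) and (D − ⌈m/2⌉)/D (missed in pairs).

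| Tablets taken | By count | m | Lowest by day | Highest by day |
|---|---|---|---|---|
| 101 | 101/112 = 90.2% | 11 | 45/56 = 80.4% | 50/56 = 89.3% |
| 100 | 100/112 = 89.3% | 12 | 44/56 = 78.6% | 50/56 = 89.3% |
| 90 | 90/112 = 80.4% | 22 | 34/56 = 60.7% | 45/56 = 80.4% |

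The count does not fix the day-based figure. The reverse problem also exists. Fourteen one-tablet days and fourteen three-tablet days (with 28 correct days) total 14 + 42 + 56 = 112 tablets. That is 100% by count and 28/56 = 50% by the day rule.

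**Denominator.** A woman takes every dose for 14 days, then stops.

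- Full-schedule denominator: 14/56 = 25.0% (14/76 = 18.4% to 14/48 = 29.2%).
- Last-dose denominator: 14/14 = 100%.
- If permanent discontinuation ends her schedule, she scores 100% whether or not she stays in follow-up, and the contrast disappears.

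**Completers.** Table 2 sets treatment as Visits 4 to 6, Section 8.10.3 puts Visit 6 on the day after TRC2 menses ends, and Section 8.6.1 has the Visit 6 morning dose taken after the PK sample. Only the status of the Visit 6 day is open. Counting it as scheduled but not as an exact-dose day gives a fully compliant woman 56/57 = 98.2% in place of 100%.

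**Exposure.** A woman dosed on all 56 days, with one tablet missed on 12 of them, has 44 days under the exact-dose meaning and 56 days from first to last dose.

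**What uses these figures.** Sections 9.11 and 9.12 lead to summary statistics in the All Participants as Treated population. The primary model in Section 9.6.1 has no compliance term. The Full Analysis Set needs one dose and one diary entry. The two deviations listed for the Per-Protocol population are diary compliance below 75% and no TRC2 pain scores. That list is not closed, but the 80% trigger in Section 6.4 applies to the site tablet count, and no analysis applies a cut-off to the Section 9.11 percentage.

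**What other text supplies.** The first double-blind dose is given at the site at Visit 4. The sSAP already uses the last dose day as a boundary for the post-treatment cycle (3.6.1) and for the TRC2 safety period (3.6.2), so the plan depends on that date whatever happens to Section 9.11. Section 8.5 defines overdose of blinded drug as more than two tablets in a day, so sites need some day-level information on excess dosing, although this does not show that a daily log exists. Sections 8.1.4, 8.1.6.1 and 10.1.8 refer to eCRF and data-management documents that are not available here.

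**The case for a change.** The best case for a change is that the repair is cheap and the sSAP was the place for it. That document exists to add derivations, and it spells out numerator, denominator and dates for diary compliance (3.5.1), yet for dosing it only repeats the protocol.

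The ambiguity might also fall unevenly between arms. Section 4.3.3 reports that 10% of participants on 50 mg bid in an earlier cough study stopped for altered taste. Suppose the same share stops here on the active arm, all after 14 compliant days of 56, and all stay in follow-up. The active-arm mean then differs by 0.10 × (100% − 25%) = 7.5 percentage points between the two denominators.

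Much of this stands. No daily study-drug record is described, the denominator has two readings for women who stop drug, and the exposure term could be clearer. The 7.5 points rest on three stacked assumptions, but the direction is plausible.

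It does not show that the rule is wrong. A daily dosing record elsewhere in the study documents is not ruled out, and the 60.7% figure needs every missed tablet to fall on a separate day. The site rule, the run-in criterion and the reporting summary do different jobs, so a difference in scale between them is not in itself an error.

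**Conclusion.** No change to the plan follows. The gap is in the wording of a descriptive summary, and whoever programs it must fill it before any output exists: name the dosing data, choose one denominator for early stoppers, and say what exposure counts. The first witnessed dose, the last dose date already used in the sSAP and the Visit 4 to 6 treatment period give sensible material for that.

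The larger step, a ratio of tablets taken to tablets scheduled, exchanges one weakness for another. It matches the site count but can report 100% for a woman who took the right dose on half her days. Duration from first to last dose likewise counts interruption days. Neither is clearly better than the day rule if daily data exist.

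For individual women the spread can be large: up to about 20 points between count and day rule at a count of 80.4% (80.4% − 60.7% = 19.7), and 75 points between denominators for a stop after 14 days. These figures assume a 56-day course, and the 19.7 also assumes no excess tablets. They reach no hypothesis test, power calculation or listed population criterion, and taste-related adverse event proportions do not use them. The conclusion would need another look if the compliance percentage were used to define an analysis population or to adjust an efficacy estimate; the documents plan neither.

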9.12 Extent of Exposure

The duration of treatment for each participant will be evaluated by calculating the number of days on therapy. Exposure to study intervention will be summarized using descriptive statistics (ie, mean, SD, median, minimum, and maximum) for the APaT population.

10 SUPPORTING DOCUMENTATION AND OPERATIONAL CONSIDERATIONS

10.1 Appendix 1: Regulatory, Ethical, and Study Oversight Considerations

10.1.1 Code of Conduct for Clinical Trials

Merck Sharp and Dohme Corp., a subsidiary of Merck & Co., Inc. (MSD)

Code of Conduct for Interventional Clinical Trials

I. Introduction

A. Purpose

MSD, through its subsidiaries, conducts clinical trials worldwide to evaluate the safety and effectiveness of our products. As such, we are committed to designing, implementing, conducting, analyzing and reporting these trials in compliance with the highest ethical and scientific standards. Protection of participants in clinical trials is the overriding concern in the design of clinical trials. In all cases, MSD clinical trials will be conducted in compliance with local and/or national regulations (eg, International Council for Harmonisation Good Clinical Practice [ICH-GCP]) and in accordance with the ethical principles that have their origin in the Declaration of Helsinki.

B. Scope

Highest ethical and scientific standards shall be endorsed for all clinical interventional investigations sponsored by MSD irrespective of the party (parties) employed for their execution (eg, contract research organizations, collaborative research efforts). This Code is not intended to apply to trials that are observational in nature, or which are retrospective. Further, this Code does not apply to investigator-initiated trials, which are not under the full control of MSD.

II. Scientific Issues

A. Trial Conduct

1. Trial Design

Except for pilot or estimation trials, clinical trial protocols will be hypothesis-driven to assess safety, efficacy, and/or pharmacokinetic or pharmacodynamic indices of MSD or comparator products. Alternatively, MSD may conduct outcomes research trials, trials to assess or validate various endpoint measures, or trials to determine patient preferences, etc.

The design (ie, participant population, duration, statistical power) must be adequate to address the specific purpose of the trial. Participants must meet protocol entry criteria to be enrolled in the trial.

2. Site Selection

MSD selects investigative sites based on medical expertise, access to appropriate participants, adequacy of facilities and staff, previous performance in clinical trials, as well as budgetary considerations. Prior to trial initiation, sites are evaluated by MSD personnel to assess the ability to successfully conduct the trial.

3. Site Monitoring/Scientific Integrity

Investigative trial sites are monitored to assess compliance with the trial protocol and general principles of Good Clinical Practice (GCP). MSD reviews clinical data for accuracy, completeness, and consistency. Data are verified versus source documentation according to standard operating procedures. Per MSD policies and procedures, if fraud, scientific/research misconduct, or serious GCP-noncompliance is suspected, the issues are investigated. When necessary, the clinical site will be closed, the responsible regulatory authorities and ethics review committees notified.

B. Publication and Authorship

Regardless of trial outcome, MSD commits to publish primary and secondary results of its registered trials of marketed products in which treatment is assigned, according to the prespecified plans for data analysis. To the extent scientifically appropriate, MSD seeks to publish the results of other analyses it conducts that are important to patients, physicians, and payers. Some early phase or pilot trials are intended to be hypothesis-generating rather than hypothesis testing, in such cases, publication of results may not be appropriate since the trial may be underpowered and the analyses complicated by statistical issues such as multiplicity.

MSD's policy on authorship is consistent with the recommendations published by the International Committee of Medical Journal Editors (ICMJE). In summary, authorship should reflect significant contribution to the design and conduct of the trial, performance or interpretation of the analysis, and/or writing of the manuscript. All named authors must be able to defend the trial results and conclusions. MSD funding of a trial will be acknowledged in publications.

III. Participant Protection

A. Ethics Committee Review (Institutional Review Board [IRB]/Independent Ethics Committee [IEC])

All clinical trials will be reviewed and approved by an IRB/IEC before being initiated at each site. Significant changes or revisions to the protocol will be approved by the ethics committee prior to implementation, except changes required urgently to protect participant safety that may be enacted in anticipation of ethics committee approval. For each site, the ethics committee and MSD will approve the participant informed consent form.

B. Safety

The guiding principle in decision-making in clinical trials is that participant welfare is of primary importance. Potential participants will be informed of the risks and benefits of, as well as alternatives to, trial participation. At a minimum, trial designs will take into account the local standard of care.

All participation in MSD clinical trials is voluntary. Participants enter the trial only after informed consent is obtained. Participants may withdraw from an MSD trial at any time, without any influence on their access to, or receipt of, medical care that may otherwise be available to them.

C. Confidentiality

MSD is committed to safeguarding participant confidentiality, to the greatest extent possible. Unless required by law, only the investigator, Sponsor (or representative), ethics committee, and/or regulatory authorities will have access to confidential medical records that might identify the participant by name.

D. Genomic Research

Genomic research will only be conducted in accordance with a protocol and informed consent authorized by an ethics committee.

IV. Financial Considerations

A. Payments to Investigators

Clinical trials are time- and labor-intensive. It is MSD's policy to compensate investigators (or the sponsoring institution) in a fair manner for the work performed in support of MSD trials. MSD does not pay incentives to enroll participants in its trials. However, when enrollment is particularly challenging, additional payments may be made to compensate for the time spent in extra recruiting efforts.

MSD does not pay for participant referrals. However, MSD may compensate referring physicians for time spent on chart review to identify potentially eligible participants.

B. Clinical Research Funding

Informed consent forms will disclose that the trial is sponsored by MSD and that the investigator or sponsoring institution is being paid or provided a grant for performing the trial. However, the local ethics committee may

wish to alter the wording of the disclosure statement to be consistent with financial practices at that institution. As noted above, all publications resulting from MSD trials will indicate MSD as a source of funding.

C. Funding for Travel and Other Requests

Funding of travel by investigators and support staff (eg, to scientific meetings, investigator meetings, etc.) will be consistent with local guidelines and practices.

V. Investigator Commitment

Investigators will be expected to review MSD's Code of Conduct as an appendix to the trial protocol, and in signing the protocol, agree to support these ethical and scientific standards.

